#### 3.3 Core lab

When a site suspects the occurrence of a stent fracture, the x-ray image will be sent to the Core lab for assessment.

CONFIDENTIAL INFORMATION

## 4.0 Statistical Analyses

### 4.1 Analysis Populations

The following populations will be used in the analysis of the endpoints:

1. All Subjects – All subjects receiving a VIABAHN® device with symptomatic peripheral arterial disease.

Data analyses will be implemented by using following populations:

- Efficacy: All Subjects
- Safety: All Subjects

If there are subjects who receive a VIABAHN® device with symptomatic peripheral arterial disease outside the SFA or other diseases than symptomatic peripheral arterial disease, target disease, target vessel and severe adverse event will be summarized in annual reports and a final report.

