#### 2. Purpose of surveillance study

To confirm device efficacy and safety in the clinical setting after the launch of the GORE® VIABAHN® Endoprosthesis (hereafter “VB device”) for the treatment of symptomatic peripheral arterial disease in the superficial femoral arteries.

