#### 6. Method of Surveillance Study

- 1) To make a written agreement between the participating institutions, NHG, and NHG’s outsourcing contractor on the surveillance study.
- 2) This survey will continuously enroll all patients treated for symptomatic peripheral arterial disease with this device in each of the participating institutions, except the patients who have the treatment of traumatic or iatrogenic vessel injury in thoracic, abdominal, and pelvic arteries (except the aorta, coronary, brachiocephalic, carotid, vertebral and pulmonary arteries) with VB device. The patients who have a treatment with VB device before conclusion of a contract will be enrolled to this study retrospectively.
- 3) The surveillance of the PAD patients who have a treatment with VB device is conducted in accordance with this protocol.
- 4) The surveillance of the patients who had a treatment with VB device for the disease except PAD is also

conducted in accordance with the contents stipulated in Attachment 1 of this protocol.

- 5) After one month from the procedure and on annually afterwards, the study doctor needs to submit the case report form with inputting the data to Electric Data Capture system that NHG indicates.
- 6) After one month from the procedure and on annually afterwards, representatives of NHG or the outsourcing contractor are to collect case report forms for the post-marketing surveillance study on which necessary items are filled out.
- 7) If any deficiencies of VIABAHN are recognized, the physicians responsible for the case or representatives of the outsourcing contractor will immediately report them to representatives of NHG and the GVP section of NHG will handle them appropriately.
- 8) From the approval date, an annual report will be made, reviewed, and approved by the Post-Marketing Surveillance Study team and the GVP section of NHG, and then submitted to PMDA.

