## 1.0 Introduction

This Statistical Analysis Plan (SAP) describes the statistical analyses planned to address the objectives of JPS 16-03. This SAP summarizes the analyses that will be performed to determine the safety and effectiveness of the GORE® VIABAHN® Endoprosthesis (VIABAHN®) when used for the treatment of patients with symptomatic peripheral arterial disease in superficial femoral arteries (SFA). This SAP outlines tables, figures, and listings that are included in reports for the JPS 16-03 Post-Marketing Surveillance.

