## 2.0 Study Design Overview

### 2.1 Objectives

The objectives of JPS 16-03 is to document the efficacy and safety of the VIABAHN® for the treatment of patients with symptomatic peripheral arterial disease in the SFA.

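### SAP 4.1 puts PAD outside the SFA into the patency and freedom-from-TLR estimates, although the stated objective is SFA disease

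*SAP*

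**What the plan says.** **Purpose and objective.** Protocol section 2 sets the purpose as confirming efficacy and safety "for the treatment of symptomatic peripheral arterial disease in the superficial femoral arteries". SAP 2.1 gives the objective as documenting both "for the treatment of patients with symptomatic peripheral arterial disease in the SFA". SAP 1.0 describes the scope in the same terms.

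**Enrolment and follow-up.** Protocol section 6, item 2, is wider: "This survey will continuously enroll all patients treated for symptomatic peripheral arterial disease with this device in each of the participating institutions", apart from a stated group of vessel injuries. Item 3 adds: "The surveillance of the PAD patients who have a treatment with VB device is conducted in accordance with this protocol". Item 4 sends only diseases other than PAD to Attachment 1.

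**Analysis population.** SAP 4.1 has a single population: "All Subjects – All subjects receiving a VIABAHN® device with symptomatic peripheral arterial disease". It names that population for efficacy and again for safety. The visible part of SAP 6.0 repeats All Subjects as the default for tables and figures.

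**Last paragraph of SAP 4.1.** For recipients with "symptomatic peripheral arterial disease outside the SFA or other diseases than symptomatic peripheral arterial disease", it plans that "target disease, target vessel and severe adverse event will be summarized in annual reports and a final report".

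**Estimates.** SAP 4.3 plans Kaplan-Meier estimates of primary assisted patency at 12 and 24 months and of freedom from TLR at 1, 12 and 24 months. Its visible text adds no limit on the vessel.

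**The concern.** Primary assisted patency and freedom from TLR are the only efficacy endpoints listed. If the analyst follows SAP 4.1, both are computed in every recipient with symptomatic PAD, whichever artery was treated. A reader of the final report, knowing the objective, would take them as results for the SFA. If patency or reintervention differs by vessel, the reported figure is a mixture that depends on how often participating sites used the device elsewhere.

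The last paragraph of SAP 4.1 adds uncertainty. It gives one reporting rule to two groups with opposite membership: non-PAD patients are outside All Subjects by definition, and non-SFA PAD patients are inside it. It does not say whether the summary adds to the main analyses or replaces them for the second group. The same gap touches the stent fracture estimate and the serious adverse event counts, where a reader could not tell whether the summary overlaps the main tables.

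**Working it through.** The plan gives no figure to reproduce. The rationale for 250 cases and the SAP's sample size section are redacted, and the point does not rest on them. The check is a comparison of texts, followed by an illustration of scale.

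**Step 1: who belongs where.**

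| Group | Protocol 6 follow-up | All Subjects (SAP 4.1) | Last paragraph of SAP 4.1 | Named in objective |
|---|---|---|---|---|
| SFA PAD | main protocol | in | no | yes |
| Non-SFA PAD | main protocol | in | yes | no |
| Non-PAD disease | Attachment 1 | out | yes | no |

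The middle row is the problem. The protocol divides patients by disease, PAD against non-PAD. The last paragraph of SAP 4.1 divides them into SFA PAD against everything else. Because non-SFA PAD patients follow the main protocol, they are scheduled for the same ABI (or TBI) and duplex assessments as SFA patients. Their data will therefore exist and will enter the efficacy estimates unless something removes them. No visible sentence does.

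**Step 2: possible shift in the estimate.** Let w be the share of non-SFA PAD among All Subjects, and d the difference in the event-free proportion between SFA and non-SFA patients at a given time. Ignoring differences in censoring:

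pooled = (1 − w) × SFA + w × non-SFA, so |pooled − SFA| = w × d.

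The documents give neither w nor d. Both are assumed here. Results are in percentage points:

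| Share w | d = 5 | d = 10 | d = 15 |
|---|---|---|---|
| 2% | 0.1 | 0.2 | 0.3 |
| 5% | 0.25 | 0.5 | 0.75 |
| 10% | 0.5 | 1.0 | 1.5 |
| 20% | 1.0 | 2.0 | 3.0 |

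A shift of 1 point needs w = 1/d, which is 20%, 10% or 6.7% for d of 5, 10 or 15 points.

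**Step 3: precision lost by restricting to the SFA.** With the event-free proportion held fixed, interval width is proportional to 1/√n. Removing a share w multiplies it by 1/√(1 − w):

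- w = 2%: 1/√0.98 = 1.010, or 1.0% wider
- w = 5%: 1/√0.95 = 1.026, or 2.6% wider
- w = 10%: 1/√0.90 = 1.054, or 5.4% wider
- w = 20%: 1/√0.80 = 1.118, or 11.8% wider

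These ratios do not depend on n. No absolute width is given because the efficacy n is not stated: 250 is the count of long-lesion patients at which enrolment stops, and patients with shorter lesions are enrolled too.

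**The case against.** **A reader might infer that the SAP is silent on whether non-SFA PAD enters the efficacy estimates.** It is not. SAP 4.1 assigns efficacy to All Subjects and defines All Subjects as all PAD recipients. By its letter, these patients are in. The defect is a mismatch between that rule and the objective.

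**A reader might also infer that SAP 4.1 contradicts itself, or that its last paragraph excludes these patients.** The text does not go that far. It says that certain items will be summarized, without saying that this is done separately or that anyone leaves All Subjects. An extra description of use outside the target vessel is compatible with keeping those patients in the main analysis, and events that appear both in a main count and in a subset summary are ordinary reporting. What remains is that the paragraph leaves its relation to All Subjects unexplained.

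**Redaction.** The table, dataset and output specifications in SAP sections 5 and 6 are largely blacked out, and Attachment 1 is not in the supplied text. A vessel restriction could be stated there. This limits the finding to the visible text. It does not remove the finding, because the section that defines the populations is readable and a restriction elsewhere would still need to be reconciled with it.

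**Materiality.** SAP 4.1 introduces these patients with a conditional, so there may be few or none. No visible hypothesis or performance goal would be overturned by a small shift. Both remarks stand.

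**All-comer enrolment.** Keeping All Subjects and adding results by vessel would match how patients are enrolled. That would also be transparent, but the headline figure would still describe a wider group than the objective.

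**Conclusion.** The point holds in this form: followed as written, the estimates of primary assisted patency and freedom from TLR would not describe the SFA population named in the objective if non-SFA PAD patients are enrolled. The issue is mainly whom the estimate describes. Its numerical size cannot be established from the documents. The range of 0.1 to 3.0 points rests wholly on an assumed 2-20% share and an assumed difference of 5-15 points, and its upper end needs both at their extremes. The conclusion is conditional on no restriction being stated in the redacted specifications. It deserves correction because these are the only efficacy endpoints and the change is small, but nothing shows that the results would be materially wrong.

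**What to change.** In SAP 4.1:

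1. Define an SFA PAD population: recipients with symptomatic PAD treated in the SFA.
2. Report the main Kaplan-Meier estimates of primary assisted patency and freedom from TLR in that population. Show the all-PAD estimate as supportive if wanted.
3. Keep stent fracture and serious adverse events in all PAD recipients, shown by SFA and non-SFA.
4. State that, for non-SFA PAD patients, the summary in the last paragraph is a subset of those safety counts.

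If the redacted specifications already restrict the efficacy tables, carry that rule into 4.1 so that the two agree.

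The cost is a few sentences and no new data, since target vessel is already to be summarized. The downside is a slightly smaller efficacy n, with the loss of precision shown in step 3 of the working.

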### 4.2 Timing of Analyses

Annual reports will be created on the anniversary of the approval date. A final analysis will be performed after all enrolled subjects complete the 60-month follow-up or have been withdrawn from the surveillance.

### 4.3 Data analysis

*Primary assisted patency*

Primary assisted patency is defined as hemodynamic evidence of flow through a device that had not required target lesion revascularization to restore flow after total occlusion. This will be estimated at 12 and 24 months by Kaplan-Meier analysis.

CONFIDENTIAL INFORMATION

### *Freedom from Target Lesion Revascularization*

Target Lesion Revascularization (TLR) is defined as repeat intervention performed at initial VIABAHN® implantation site of the study limb to maintain or re-establish patency. This will be estimated at 1, 12, and 24 months after implant by Kaplan-Meier analysis.

Term	Percentage
GMOs	~75%
Organic	~95%
Natural	~85%
Artificial	~55%
Organic	~90%
Natural	~80%
Artificial	~60%
Organic	~80%
Natural	~70%
Artificial	~45%
Organic	~70%
Natural	~60%
Artificial	~35%
Organic	~60%
Natural	~50%
Artificial	~30%
Organic	~50%
Natural	~40%
Artificial	~25%

#### *Occurrence of device or procedure related serious adverse events*

The number of subjects for which a reported serious adverse event occurred will be calculated at procedure and 1, 12, 24, 36, 48, and 60 months after implant.

If deficiencies occurred, the detail will be reported in annual reports and a final report.

Serious adverse events (SAE), regardless of their causal relationship, are the events that fall under these categories:

- 1) Death
- 2) A case in which the event is suspected to cause a life-threatening condition.
- 3) A case that requires hospitalization in a hospital or a clinic or an extension of a hospital stay.
- 4) Disability
- 5) A case in which the event could have resulted in disability.
- 6) A case that is serious according to the cases in the above 1 to 5.
- 7) A congenital disease or abnormality from which a later generation of a patient will suffer.

An SAE is classified by the physician who is responsible for the subject.

Hospitalization without the onset of a new adverse event or aggravation of a pre-procedure complication, such as the reasons for hospitalization listed below, will not be handled as a serious adverse event.

CONFIDENTIAL INFORMATION

- Hospitalization due to treatment that had previously been scheduled before the procedure to implant VIABAHN® (i.e., hospitalization due to surgery for a pre-procedure complication that can be conducted after improvement of the target lesion).
- Administrative hospitalization (e.g. hospitalization for a regular medical checkup, examination, or training).
- Hospitalization at a rehabilitation facility.

#### *Stent fracture*

Stent fracture rates will be estimated at 12, 24, 36, 48 and 60 months by Kaplan-Meier analysis. When an occurrence of fracture is suspected at the site, the image will be sent to Core lab for assessment.

## 5.0 Analysis Specifications

### 5.1 SAS Analysis Dataset Specifications

CONFIDENTIAL INFORMATION

## 5.2 Statistical Output Specifications

[REDACTED]

[REDACTED]

[REDACTED]

[REDACTED]

[REDACTED]

[REDACTED]

[REDACTED]

[REDACTED]

## 5.3 Verification Level for Statistical Output

[REDACTED]

- All Analysis Datasets – Level I
- All Tables – Level I
- All Listings – Level II

## 6.0 Data Sets, Tables, Figures, and Listings

At a minimum, the follow set of Tables and Figures will be produced for the reports defined in section 4.2. Unless specified, the Tables and Figures will be analyzed using [REDACTED] All Subjects [REDACTED]

[REDACTED] Listings will be produced for the final report.

### 6.1 Analysis Tables

[REDACTED]

[REDACTED]

[REDACTED]

[REDACTED]

CONFIDENTIAL INFORMATION

A series of 15 horizontal black bars of varying lengths, decreasing from left to right, representing a data distribution.

## 6.2 Analysis Listings

Term	Percentage
GMOs	~75%
Organic	~90%
Natural	~85%
Artificial	~60%
Organic	~80%
Natural	~75%
Artificial	~65%
Organic	~85%
Natural	~80%
Artificial	~60%
Organic	~95%
Natural	~90%
Artificial	~70%

## 6.3 Analysis Figures

Three horizontal black bars of decreasing length from top to bottom, positioned above the title text.

